5.4.7 Management of new or worsening pulmonary symptoms

If new or worsening pulmonary symptoms (e.g. dyspnea) or radiological abnormalities occur in the absence of a clear diagnosis, an interruption in all study treatment dosing is recommended and further diagnostic workup (including a high-resolution CT scan) should be performed to exclude pneumonitis. In cases of confirmed pneumonitis (as known toxicity with olaparib), treatment is to discontinue.

The following assessments, and additional assessments if required, will be performed to enhance the investigation and diagnosis of potential cases of pneumonitis. The results of the assessment will be collected.

- Physical examination; Signs and symptoms (cough, shortness of breath, pyrexia, etc.) including auscultation for lung field will be assessed.
- SpO₂; Saturation of peripheral oxygen (SpO₂)
- Other items; When pneumonitis (interstitial lung disease [ILD]) is suspected during study treatment, the following markers should be measured where possible:
 - ILD markers (KL-6, SP-D) and β-D-glucan
 - PSA

Following investigation, if no evidence of abnormality is observed on CT imaging and symptoms resolve, then study treatment can be restarted at the same dosing, if deemed appropriate by the Investigator. If significant pulmonary abnormalities are identified, these need to be discussed with the Study Physician.

5.4.8 Management of nausea and vomiting

As per international guidance on anti-emetic use in cancer patients (ESMO, NCCN), generally a single agent antiemetic should be considered (e.g. dopamine receptor antagonist, antihistamines or dexamethasone).

Events of nausea and vomiting are known to be associated with olaparib treatment. These events are generally mild to moderate (CTCAE grade 1 or 2) severity, intermittent and manageable on continued treatment. The first onset generally occurs in the first month of treatment for nausea and within the first 6 months of treatment for vomiting. For nausea, the incidence generally plateaus at around 9 months, and for vomiting at around 6 to 7 months.

No routine prophylactic anti-emetic treatment is required at the start of study treatment, however, patients should receive appropriate anti-emetic treatment at the first onset of nausea or vomiting and as required thereafter, in accordance with local treatment practice guidelines. Alternatively, olaparib tablets can be taken with a light meal/snack (i.e. 2 pieces of toast or biscuits). See section 5.4.6 for exclusion criteria to Grade 4 trial discontinuation.

5.4.9 Management of diarrhea

Vigorous anti-diarrheal treatment loperamide (Imodium) is required at the first onset of diarrhea according to American Society of Clinical Oncology (ASCO) guidelines unless systemic infection is suspected and requires rule out per treating physician. Oral loperamide (Imodium) should be used first and with repeat episodes per package guidelines. The first dose of loperamide may be lowered to 2 mg if the diarrhea is recurrent and if in the opinion of the treating physician, the diarrhea is not severe.

Patients should be instructed to notify the Investigator or research staff of the occurrence of bloody or black stools, symptoms of dehydration, fever, inability to take liquids by mouth, and inability to control diarrhea within 24 hours of using loperamide or other prescribed anti-diarrheal medications.

If diarrhea is severe (i.e. requiring intravenous [IV] rehydration) and/or associated with fever or severe neutropenia (Grade 3 or 4), broad-spectrum antibiotics must be prescribed. Patients with severe diarrhea or any diarrhea associated with severe nausea or vomiting should be hospitalized for IV hydration and correction of electrolyte imbalances per provider discretion. Doses should be held for Grade 3 or 4 toxicity. See section 5.4.6 for exclusion to Grade 4 trial discontinuation regarding diarrhea.

5.4.10 Renal toxicity

If subsequent to study entry and while still on study therapy, a patient's estimated CrCl falls below the threshold for study inclusion (≥ 51 mL/min), retesting should be performed promptly.

A one step dose reduction is recommended for patients who develop moderate renal impairment (calculated CrCl by Cockcroft-Gault equation of between 31 and 50 mL/min) for any reason during the course of the study: the dose of olaparib should be reduced to 200 mg BID, see Table 2.

Olaparib has not been studied in patients with severe renal impairment ($\text{CrCl} \leq 30 \text{ mL/min}$) or end-stage renal disease; if patients develop severe impairment or end stage disease is it recommended that olaparib be discontinued.

5.4.11 Management of hepatic toxicity

Drug should be stopped if

- ALT or AST or ALP* $> 5 \times \text{ULN}$
- ALT or AST or ALP* $> 3 \times \text{ULN}$ with the appearance of symptoms associated with a clinical diagnosis of hepatitis including right upper quadrant pain or tenderness, fever, rash or eosinophilia ($> 5\%$)
- [ALT or AST $> 3 \times \text{ULN}$] and [total bilirubin $> 2 \times \text{ULN}$ or INR > 1.5 (unless patient is receiving warfarin) or other evidence of impairment to the synthesis function of the liver]
* In the presence of bone metastasis, assess bone specific isoform of raised ALP in the presence of a raised gamma-GT (to ensure the ALP change is specific to the liver).

Please refer to Appendix A “Actions Required in Cases of Combined Increase of Aminotransferase and Total Bilirubin - Hy’s Law”.

5.4.12 Management of cardiovascular abnormalities

Cardiovascular toxicity is potentially associated with AZD6738. Either clinically significant hypotension (defined as an asymptomatic decrease of more than 20 mmHg in systolic blood pressure to below 70 mmHg persisting for at least 10 minutes) or symptomatic orthostatic fall in systolic blood pressure (of more than 20 mmHg compared to resting supine systolic blood pressure) should be managed with drug interruptions or reductions as per investigator’s discretion.

5.4.13 Drug interruptions for intercurrent non-toxicity related events

Study treatment dose interruption for conditions other than toxicity resolution should be kept as short as possible. If a patient cannot restart study treatment within 28 days for resolution of intercurrent conditions not related to disease progression or toxicity, the case should be discussed with the Study Physician. All dose reductions and interruptions (including any missed doses), and the reasons for the reductions/interruptions are to be recorded in the eCRF.

Study treatment should be stopped at least 3 days prior to planned surgery and restarted 10 days post-surgery if the wound has healed. If the wound has not healed well, a further 7 days may be allowed and the patient can recommence study drug(s) if there is no evidence of disease progression. No stoppage of study treatment is required for any needle biopsy procedure. Study treatment should be discontinued for a minimum of 3 days before a patient undergoes palliative radiation treatment. Study treatment should be restarted within 4 weeks as long as any bone marrow toxicity has recovered.

Because the AEs related to olaparib may include asthenia, fatigue and dizziness, patients should be advised to use caution while driving or using machinery if these symptoms occur.

TABLE 4 Dose interruption and stopping criteria

Event	Action
Surgery	Interrupt both drugs (maximum 28 days) and resume at full dose. Both drugs should be stopped 3 days prior to surgery and resumed approximately 10 days later. If the wound has not healed a further 7 days are permitted prior to restarting combination. No stoppage is required for biopsy procedures.
Vomiting	If vomiting occurs shortly after study medication is swallowed, the dose should only be replaced if all of the intact tablets can be counted. Resume with the following scheduled dose.
Missed dose	Allowed to take the scheduled dose up to 2 hours after the scheduled dose time. If greater than 2 hours, the missed dose should not be taken and patient should continue with next dose at allotted time.

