ID: UMCC 2018.108

NCT03787680

**Targeting Resistant Prostate Cancer With ATR
and PARP Inhibition (TRAP Trial)**

Drug Substance	AZD6738
Study Number	UMCC 2018.108
Version Number	4.1
Date	27JUN2023

A Multi-Center Phase II Study Testing the Activity of Olaparib and AZD6738 (ATR Inhibitor) in Metastatic Castration-Resistant Prostate Cancer.

Short Title: Targeting Resistant prostate cancer with ATR and PARP inhibition (TRAP trial)

PROTOCOL SYNOPSIS

A Multi-Center Phase II Study Testing the Activity of Olaparib and AZD6738 (ATR Inhibitor) in Metastatic Castration-Resistant Prostate Cancer.

Principal Investigator/Sponsor-Investigator

[name]., Ph.D.

University of Michigan, Department of Medical Oncology
[name]
[name]
[contact]
[contact]
Email: [contact]

IND: 141954

Coordinating Center: University of Michigan

Biostatistician

[name]
University of Michigan
[name]
[name]
[name]
[contact]
Email: [contact]

Study site(s) and number of subjects planned

The study will enroll 47 evaluable patients from 4 academic centers.

Study period	Phase of development
Estimated date of first subject enrolled	1/2019
Estimated date of last subject completed	4/2021

Study design

This is a phase II Simon 2-stage study evaluating the response rate for the combination of AZD6738 (ceralasertib) and olaparib for patients with metastatic castration-resistant prostate cancer (mCRPC) who are DNA repair proficient (DRPro) and deficient (DRDef). Patients are DRDef based on somatic mono- or bi-allelic loss of ATM, somatic biallelic loss of either BRCA1 or BRCA2 OR known mono- or biallelic germline loss in ATM, BRCA1 or BRCA2.

Objectives

Primary Objectives:	Outcome Measures:
To determine the response rate of the combination of olaparib and AZD6738 in mCRPC patients who are DNA repair proficient (DRPro, e.g. intact ATM, BRCA1 and BRCA2).	The rate of response (CR/PR) per radiographic response according to RECIST v1.1 or PSA ($\geq 50\%$ decline) in DRPro patients.

Secondary Objective:	Outcome Measure:

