5.4.2 Dose levels for olaparib and AZD6738

Both drugs have two levels allowed for dose reductions and may be dose reduced stepwise per instructions below. Once a dose is reduced, escalation is not permitted. All dose modification and interruptions (including any missed doses) and the reasons for the modifications/interruptions are to be recorded in the eCRF. Repeat dose interruptions are allowed as required, for a maximum of 4 weeks on each occasion.

AZD6738 has a unique aspect in that its hematologic toxicity (specifically neutropenia, leukopenia, thrombocytopenia, see section 5.4.5) is schedule rather than dose-dependent. For hematologic toxicities related to AZD6738 requiring a single dose reduction, the schedule is adjusted rather than the daily dose (see Table 1). Non-hematologic toxicities requiring dose reductions (as both drugs would be lowered by one level), daily dose is lowered rather than schedule. If both a hematologic (related to AZD6738 per 5.4.5) AND non-hematologic Grade 3+ toxicity requiring dose reduction occur concurrently, both drugs are dose reduced. Olaparib is reduced by one dose level, while if AZD6738 is on dose level 0 is reduced to dose level -2 at first reduction.

TABLE 1 Dose Modification Table for AZD6738

Dose Level	AZD6738
0	160 mg daily Days 1-7
-1 (Hematologic toxicity)	160 mg daily Days 1-4
-1 (Non-hematologic toxicity)	120 mg daily Days 1-7
-2	120 mg daily Days 1-4

TABLE 2 Dose Modification Table for Olaparib

Dose Level	Olaparib
0	300 mg BID Days 1-28
-1	250 mg BID Days 1-28
-2	200 mg BID Days 1-28

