5.4.4 Management of anemia

Olaparib has shown the most suppression of red blood cells in prior studies, such that it is first reduced in lower risk anemia scenarios. At development of anemia, appropriate supportive treatment should be considered (per local guidelines) and alternate cause evaluation considered (e.g. iron, vitamin B12, folate, hypothyroidism). Investigator judgement to continue study treatment with or without supportive treatment (e.g. transfusion) or interrupt dose for a maximum of 4 weeks per guidance below. The use of erythropoietin is not allowed. For cases where patients develop prolonged hematologic toxicity causing >2-week interruption/delay in study treatment for CTCAE Grade 3 or worse anemia and/or blood transfusion dependence, refer to Section 5.4.14 for workup to consider.

Note, if at any time a dose reduction for a drug is required and the patient is already at dose level -2 for that drug, the patient must be removed from study.

Symptoms related to the Anemia (e.g. fatigue, shortness of breath) are designated by treating provider.

ASYMPTOMATIC Grade 2 Anemia (Hgb<10 and Hgb≥8 g/dL):

Asymptomatic Grade 2 anemia may be monitored and treatment continued without required delay or dose reduction. Delay, dose reduction and transfusions may be done at provider's discretion.

SYMPTOMATIC Grade 2 Anemia (Hgb<10 and Hgb≥8 g/dL) or ANY Grade 3 Anemia (Hgb<8 g/dL):

First episode:

1. Symptomatic Grade 2:

A treatment delay up to 28 days maximum (with or without blood transfusion) to allow resolution to asymptomatic Grade 2, Grade 1 or lower. Olaparib may be dose reduced or continued at current dose level.

2. Grade 3:

Treatment is delayed to allow resolution to asymptomatic Grade 2, Grade 1 or lower (up to 28 days maximum). Transfusions may be done at provider's discretion. Upon recovery, olaparib is reduced by one dose level (if possible).

Second episode:

3. Symptomatic Grade 2:

A treatment delay up to 28 days maximum (with or without transfusion) to allow resolution to asymptomatic Grade 2, Grade 1 or lower. Upon recovery, Olaparib is dose reduced by one level (if possible).

1. If olaparib was at full dose, AZD6738 dose/schedule is unchanged.
2. If olaparib was at dose level -1, AZD6738 is moved down one dose level. Either from dose level 0 to dose level -1 (hematologic toxicity, which is 160 mg daily Days 1-4) OR from dose level -1 (hematologic or non-hematologic) to dose level -2.

4. Grade 3:

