11. IMPORTANT MEDICAL PROCEDURES TO BE FOLLOWED

11.1 Overdose

There is currently no specific treatment in the event of overdose with AZD6738 and possible symptoms of overdose are not established.

AZD6738 must only be used in accordance with the dosing recommendations in this protocol. Any dose or frequency of dosing that exceeds the dosing regimen specified in this protocol should be reported as an overdose. The Maximum Tolerated Dose is 160 mg by mouth daily for 7 out of 28 days for AZD6738 and 300 mg by mouth twice a day for olaparib.

Adverse reactions associated with overdose should be treated symptomatically and should be managed appropriately.

There is currently no specific treatment in the event of overdose with olaparib and possible symptoms of overdose are not established. *Olaparib* must only be used in accordance with the dosing recommendations in this protocol. Any dose or frequency of dosing that exceeds the dosing regimen specified in this protocol should be reported as an overdose. The Maximum Tolerated Dose is 300 mg twice daily (tablet).

Adverse reactions associated with overdose should be treated symptomatically and should be managed appropriately.

An overdose with associated AEs is recorded as the AE diagnosis/symptoms on the relevant AE modules in the eCRF and on the Overdose CRF module.

An overdose without associated symptoms is only reported on the Overdose CRF module.

If an overdose on an AstraZeneca study drug occurs in the course of the study, then investigators or other site personnel should inform the Coordinating Center **within one day**, i.e., immediately but no later than **the end of the next business day** of when he or she becomes aware of it. The Coordinating Center will send the information within 24 hours of receipt to AstraZeneca Patient Safety.

The designated AstraZeneca representative works with the Coordinating Center to ensure that all relevant information is provided to the AstraZeneca Patient Safety data entry site.

For overdoses associated with SAE, standard reporting timelines apply, see Section 7.7. For other overdoses, reporting should be done within 30 days.

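### The surgery row of Table 4 restarts both drugs at full dose with no exception for patients already reduced, contrary to the no-escalation rule in Section 5.4.2

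*Combined protocol and SAP*

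**What the plan says.** Section 5.4.2 sets the dose ladder for both drugs in Tables 1 and 2 (level 0, the starting dose, then levels -1 and -2) and adds a general rule: "Once a dose is reduced, escalation is not permitted". It makes no exception for restarts after an interruption.

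Section 5.4.13 covers interruptions for reasons other than toxicity. Its running text gives the timing around an operation: "Study treatment should be stopped at least 3 days prior to planned surgery and restarted 10 days post-surgery if the wound has healed". It allows a further 7 days if the wound has not healed, and names no dose. The dose appears only in the surgery row of Table 4: "Interrupt both drugs (maximum 28 days) and resume at full dose". The row neither mentions patients who have already been reduced nor refers back to Section 5.4.2.

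**The concern.** For a patient still at level 0 the two rules agree. For a patient already at level -1 or -2 they give opposite instructions. A site that follows Table 4 as written raises the dose; a site that follows Section 5.4.2 keeps it where it was. The protocol does not say which rule takes precedence.

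The stake is safety in a small group. These patients did not tolerate the starting dose of at least one drug, and they would return to it about 10 days after an operation. Section 11.1 describes that dose as the upper limit: "The Maximum Tolerated Dose is 160 mg by mouth daily for 7 out of 28 days for AZD6738", with the matching statement for olaparib at 300 mg twice daily. Section 5.4.3 expects hematologic toxicity to be the main difficulty, and Section 5.4.14 states that any prolonged marrow effect of AZD6738 is unknown. The row also reaches patients put on olaparib 200 mg twice daily for moderate renal impairment under Section 5.4.10.

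There is a second consequence. Sections 5.4.4 to 5.4.6 remove a patient who needs a further reduction when already at level -2. After a literal re-escalation, the protocol does not say where that patient stands on the ladder, so the participating centers could handle the next toxicity differently.

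**Working it through.** The plan gives no figure on this point to reproduce. The check has three parts: what full dose means in this protocol, how large the dose change would be, and how many patients could meet the conflict.

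**1. Meaning of full dose.** The protocol does not define the term, so its use elsewhere has to decide.

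- Section 5.4.4, second episode of symptomatic Grade 2 anemia, separates two states. Item 1: "If olaparib was at full dose, AZD6738 dose/schedule is unchanged". Item 2: "If olaparib was at dose level -1, AZD6738 is moved down one dose level". Full dose is therefore the state that is not level -1, namely level 0.
- Where the patient's own level is meant, the wording differs. Section 5.4.4 (first episode) refers to the *current* dose level, Section 5.4.7 (restart after a pulmonary work-up) to the *same* dosing, and Appendix B (after a CYP3A inhibitor) to the full *prior* dose. Table 4 has no such qualifier.

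The most natural literal reading of the row is a restart at level 0.

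**2. Size of the dose change.** Inputs are Tables 1 and 2 in Section 5.4.2.

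- Olaparib per cycle = mg per dose × 2 doses per day × 28 days.
- AZD6738 per cycle = mg per day × number of dosing days.
- Ratio = level 0 total ÷ reduced-level total.

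| Drug and level | Calculation | mg per cycle | Level 0 ÷ this level |
|---|---|---|---|
| Olaparib 0 | 300 × 2 × 28 | 16,800 | 1 |
| Olaparib -1 | 250 × 2 × 28 | 14,000 | 1.2 |
| Olaparib -2 | 200 × 2 × 28 | 11,200 | 1.5 |
| AZD6738 0 | 160 × 7 | 1,120 | 1 |
| AZD6738 -1, non-hematologic | 120 × 7 | 840 | 1.33 |
| AZD6738 -1, hematologic | 160 × 4 | 640 | 1.75 |
| AZD6738 -2 | 120 × 4 | 480 | 2.33 |

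Every ratio in a reduced row exceeds 1, so each such restart is an escalation of the kind that Section 5.4.2 forbids.

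**3. Patients who could meet the conflict.** The Synopsis gives the sample: "The study will enroll 47 evaluable patients from 4 academic centers". The documents give no rate of dose reduction or of surgery on treatment. Both rates below, and their independence, are assumptions.

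Expected number = 47 × proportion reduced × proportion having surgery.

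| Case | Reduced | Surgery | Expected patients |
|---|---|---|---|
| Low | 20% | 2% | 47 × 0.20 × 0.02 = 0.19 |
| Middle | 40% | 5% | 47 × 0.40 × 0.05 = 0.94 |
| High | 60% | 10% | 47 × 0.60 × 0.10 = 2.82 |

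The temporary olaparib doses for CYP3A inhibitors in Appendix B are a separate, stated exception and play no part in this comparison.

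**The case against.** The strongest reply is that the two rules can be read together. Section 5.4.2 is the section on dose levels and is unqualified. Table 4 belongs to a section on interruptions unrelated to toxicity, so its row may mean only that an operation is not itself a reason to reduce. It does not claim to override Section 5.4.2, and a careful site would probably apply the no-escalation rule. The meaning of full dose is inferred, mainly from one contrast in the anemia rules, and Appendix B shows that the word full can also describe a patient's own earlier dose.

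The reply also points to safeguards: ANC and platelet thresholds on Day 1 of every cycle, the rules for interruption, reduction and removal, and source-verified records of dose changes. It adds that level 0 is every patient's planned starting dose, and that the patient count rests entirely on assumed rates.

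Much of this stands. The benign intent is plausible, the safeguards would limit harm, and the count is only indicative. It is also right that Section 5.4.2 bears on the restart dose, so Table 4 is the only surgery-specific text on that dose rather than the only text that applies. But that overlap is the conflict itself. The benign reading is not written anywhere, no order of precedence is given, and the protocol's own usage favors the literal reading. The safeguards act only after a wrong dose has been given or toxicity has recurred; they do not tell a site which dose to dispense.

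**Conclusion.** The surgery row is wrong as written, though narrow in scope. Followed literally, it takes a reduced patient back to the starting dose: 1.2 to 1.5 times the reduced olaparib dose and 1.33 to 2.33 times the reduced AZD6738 dose per cycle. These ratios describe literal compliance, not expected practice.

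Only patients reduced before an operation on treatment are affected, probably between none and about three of 47 under the assumed rates. The sample size, error rates, power and planned efficacy analysis do not change. The point should be fixed because it is a contradiction in a dosing instruction whose literal reading leads to the higher dose.

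**What to change.** Reword the Table 4 surgery row so that both drugs are interrupted for at most 28 days and then resumed *at the dose level in use before the interruption; surgery itself requires no dose reduction*. The timing text in the row can stay. This keeps the probable intent, agrees with Section 5.4.2 (which needs no edit), and leaves patients at level 0 exactly where they are now.

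The cost is one phrase in one table row at the next amendment, with no added patients, visits or data.

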5.4.14 Management of prolonged hematologic toxicities while on study treatment

If a patient develops prolonged hematological toxicities (due to either AZD6738 or olaparib or both drugs) such as:

- ≥ 2 -week interruption/delay in study treatment due to CTCAE Grade 3 or worse anemia and/or development of blood transfusion dependence
- ≥ 2 -week interruption/delay in study treatment due to CTCAE Grade 3 or worse neutropenia (ANC $< 1 \times 10^9/L$).
- ≥ 2 -week interruption/delay in study treatment due to CTCAE Grade 3 or worse thrombocytopenia and/or development of platelet transfusion dependence (Platelets $< 50 \times 10^9/L$).

Check weekly differential blood counts including reticulocytes and peripheral blood smear for prolonged hematologic toxicities requiring delays. If any blood parameters remain clinically abnormal after 4 weeks of dose interruption, the patient should be referred to hematologist for further investigations. Bone marrow analysis and/or blood cytogenetic analysis should be considered at this stage according to standard hematological practice. Study treatment should be discontinued if blood counts do not recover to CTCAE Grade 1 or better within 4 weeks of dose interruption.

Development of a confirmed MDS or other clonal blood disorder should be reported as an SAE and full reports must be provided by the Investigator to AstraZeneca Patient Safety. Study treatment should be discontinued if patient's diagnosis of MDS and/or AML is confirmed. The effect if any of AZD6738 on the bone marrow in terms of prolonged suppression is unknown.

Bone marrow or blood cytogenetic samples may be collected for patients with prolonged haematological toxicities as defined in Section above. Bone marrow analysis should include an aspirate for cellular morphology, cytogenetic analysis and flow cytometry, and a core biopsy for bone marrow cellularity. If it is not possible to conduct cytogenetic analysis or flow

cytometry on the bone marrow aspirate, then attempts should be made to carry out the tests on a blood sample. Full reports must be provided by the investigator for documentation on the Patient Safety database. These data are not required to be entered into CRF.

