5.4 Management of Toxicity

5.4.1 Toxicities that require discontinuation from protocol therapy

Any toxicity observed during the course of the study should be managed in the first instance by interruption of the dose of study treatment and dose reductions if necessary. Repeat dose interruptions are allowed as required for a maximum of 28 days on each occasion. Treatment must be interrupted until the patient recovers completely or the toxicity reverts to NCI CTCAE grade 1 or 2 (depending on toxicity) or to the baseline CTCAE grade. If the required interruption is any longer than 28 days due to toxicity, the patient must be removed from the study. If at any point during study treatment, it becomes apparent that the tumor is not coming under control, patients are to be removed from study and treated as clinically indicated.

Protocol therapy should be discontinued if a patient experiences:

- Any CTCAE Grade 4 toxicity with the exception of:
 - CTCAE Grade 4 neutropenia of 5 days or fewer duration
 - CTCAE Grade 4 nausea, vomiting or diarrhea that resolves to Grade 3 in less than 72 hours in patients who have not received optimal anti-emetic or anti-diarrheal therapy
 - CTCAE Grade 4 laboratory abnormalities that can be readily corrected within 72 hours and do not result in hospitalization
- CTCAE Grade 3 or 4 thrombocytopenia with bleeding requiring hospitalization

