Treatment is delayed to allow resolution to asymptomatic Grade 2, Grade 1 or lower (up to 28 days maximum). Transfusions may be done at provider's discretion. Upon recovery, olaparib is reduced by one dose level (if possible).

1. AZD6738 is moved down one dose level. Either from dose level 0 to dose level -1 (hematologic toxicity, which is 160 mg daily Days 1-4) OR from dose level -1 (hematologic or non-hematologic) to dose level -2.

Third episode:

5. Symptomatic Grade 2 or Grade 3:

A treatment delay up to 28 days maximum (with or without transfusion) to allow resolution to asymptomatic Grade 2, Grade 1 or lower. Upon recovery, Olaparib is dose reduced by one level (if possible).

1. AZD6738 is moved down one dose level to dose level -2 (if possible).

If no further reductions are possible because olaparib or AZD6738 are already at dose level -2, the patient should be removed from the study.

Fourth episode:

6. Symptomatic Grade 2: Patient is removed from study
7. Grade 3: Patient is removed from study

Any episode of Symptomatic Grade 2 or Grade 3 anemia in conjunction with Grade 2 or higher neutropenia, leukopenia or thrombocytopenia

Treatment is delayed to allow resolution of anemia to asymptomatic Grade 2, Grade 1 or lower and thrombocytopenia/leukopenia/neutropenia to Grade 2 or lower (up to 28 days maximum). Provider may do transfusions at their discretion. Upon resumption of therapy, olaparib is dose reduced by one level. AZD6738 is dose reduced by one dose level. Either from dose level 0 to dose level -1 (hematologic toxicity, which is 160 mg daily Days 1-4) OR from dose level -1 (hematologic or non-hematologic) to dose level -2.

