5.4.5 Management of neutropenia, leukopenia and thrombocytopenia

Adverse events of neutropenia and leukopenia should be managed as deemed appropriate by the Investigator with close follow up and interruption of study drug if CTCAE Grade 3 or higher occurs. For toxicity of Grades 1-2, especially if more than one toxicity is present, drug can be interrupted at Investigator discretion. Interruption can be up to a maximum of 4 weeks. Appropriate supportive treatment and causality should be considered. For CTCAE grade 3-4 toxicities, dose interruption until recovered to grade 1 or 2 or better (up to a maximum of 4 weeks) should be done. If repeat occurrences, then dose reduce olaparib to dose level -1 and AZD6738 to dose level -1 (hematologic) per above. If a second event happens, dose reduction of olaparib to dose level -2 and AZD6738 to dose level -2 should be done. If either dose does not have another dose level below, they should be removed from study.

G-CSF should be given according to local hospital guidelines for febrile neutropenia but not within 24 hours of the last dose of study treatment unless absolutely necessary. Primary prophylaxis with G-CSF is not allowed. After G-CSF, treatment can resume at the earliest 24 hours after last G-CSF dose OR 7 days for pegylated G-CSF.

For cases where patients develop prolonged hematological toxicity (>2-week interruption/delay in study treatment due to CTCAE Grade 3 or worse), refer to Section 5.4.14.

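### A patient still at Grade 2 when a prolonged hematologic hold reaches 4 weeks must stop treatment under 5.4.14 but may resume under 5.4.4 or 5.4.5

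*Combined protocol and SAP*

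**What the plan says.** Four parts of the protocol bear on this.

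- **5.4.14 (prolonged hematologic toxicity).** The listed triggers are a hold of at least 2 weeks for anemia, "interruption/delay in study treatment due to CTCAE Grade 3 or worse anemia and/or development of blood transfusion dependence", for neutropenia, "interruption/delay in study treatment due to CTCAE Grade 3 or worse neutropenia", and the equivalent for thrombocytopenia. The stopping sentence is: "Study treatment should be discontinued if blood counts do not recover to CTCAE Grade 1 or better within 4 weeks of dose interruption".
- **5.4.4 (anemia).** For Grade 3 anemia: "Treatment is delayed to allow resolution to asymptomatic Grade 2, Grade 1 or lower (up to 28 days maximum"). Then, at the first and second episodes: "Upon recovery, olaparib is reduced by one dose level (if possible"). The section gives the range for the asymptomatic Grade 2 state: "ASYMPTOMATIC Grade 2 Anemia (Hgb<10 and Hgb≥8 g/dL"). For Grade 3 holds beyond 2 weeks it points to 5.4.14, but only for investigations the site might consider.
- **5.4.5 (neutropenia, leukopenia, thrombocytopenia).** For Grade 3-4 events: "dose interruption until recovered to grade 1 or 2 or better (up to a maximum of 4 weeks) should be done". It also refers holds of more than 2 weeks to 5.4.14, without saying what changes there.
- **10.3.4 (early stopping).** Once 10 patients are enrolled, enrollment halts if more than 25% have been removed for toxicity. Excessive toxicity is defined as removal that occurs even though the dose was modified.

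**The concern.** Sections 5.4.4 and 5.4.5 set a recovery target of Grade 2 for the full 4 weeks. Section 5.4.14 sets Grade 1 at the same deadline for a subset of the same patients, and the consequence of missing it is the end of treatment. Section 5.4.3 names hematologic toxicity as the main difficulty expected, and four centers will apply these rules. Two sites following the protocol could keep one patient and remove another in the same clinical state. Whether a patient stays on treatment, and possibly whether he enters the toxicity stopping count, would then depend on which section the site read.

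**Working it through.** The plan gives no figure to reproduce. The check sets the rules side by side and applies them to test patients.

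**Rules at the 4-week limit, for a hold of 2 weeks or more due to a Grade 3 or worse event**

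| Section | Counts as recovery | At Grade 2 when 4 weeks are reached |
|---|---|---|
| 5.4.4, anemia | Grade 2 without symptoms, or better | Resume, with the section's dose-level step |
| 5.4.5, neutropenia and thrombocytopenia | Grade 2 or better | Recovered, so resumption is implied |
| 5.4.14, prolonged toxicity | Grade 1 or better | Discontinue |

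**Test patient A (anemia).** First episode, hemoglobin below 8 g/dL, both drugs held. On day 28 hemoglobin is 9 g/dL without symptoms. Since 8 ≤ 9 < 10, this is asymptomatic Grade 2 by 5.4.4's own range.
- 5.4.4: recovered within 28 days, so he resumes with olaparib one level lower.
- 5.4.14: held at least 2 weeks for Grade 3 anemia and not at Grade 1 by 4 weeks, so he is discontinued.

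**Test patient B (neutropenia).** Grade 3, held, at Grade 2 at week 4.
- 5.4.5: recovered.
- 5.4.14: discontinued.

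**Where the conflict does not arise.** A patient who reaches Grade 2 in under 2 weeks, without transfusion dependence, never enters 5.4.14. A long hold for symptomatic Grade 2 anemia is not among its listed triggers.

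**Trigger.** 5.4.4 and 5.4.5 refer onward when the hold exceeds 2 weeks, whereas 5.4.14 starts at 2 weeks or more. A hold of exactly 14 days is inside 5.4.14 but outside both cross-references.

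**Related limit in 5.4.3.** A cycle needs an ANC of at least 1000/µL, the level that 5.4.14 puts just outside Grade 3, and platelets of at least 75,000/µL. Section 5.4.14 puts Grade 3 platelets below 50 × 10⁹/L, which is 50,000/µL. A patient between 50,000 and 75,000/µL therefore cannot start a new cycle whichever recovery grade is used, which narrows the thrombocytopenia conflict.

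**Link to 10.3.4.** Taking the rule as an observed proportion above 25% from 10 patients on:
- 2/10 = 20%, which is not above 25%: continue.
- 3/10 = 30%, which is above 25%: halt.

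With two counted removals already among 10 patients, one more patient handled under 5.4.14 rather than 5.4.4 or 5.4.5 changes the decision, provided that he counts. Patient A may not count. Under 5.4.4 his first dose reduction comes only on recovery, so at removal he has had a hold and no reduction. Sections 5.4.2 and 10.3.3 list dose modifications separately from interruptions or delays, which leans toward a hold not counting, but 10.3.4 does not settle it.

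**The case against.** The best defense is that the sections form two tiers: 5.4.4 and 5.4.5 give ordinary recovery rules, and prolonged cases pass to 5.4.14, a stricter rule for a suspected marrow problem. For neutropenia and thrombocytopenia this is plausible, because 5.4.5 refers to 5.4.14 without qualification. It is weaker for anemia, where 5.4.4 sends the reader there only for optional workup and keeps its Grade 2 target for the full 28 days. No section states precedence, so the defense offers a possible reading and does not remove the conflict.

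A reader might infer more than the text supports:

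- **That every hold of 2 weeks or more is affected.** The listed triggers in 5.4.14 require a Grade 3 or worse cytopenia or transfusion dependence.
- **That the rules clash throughout weeks 2 to 4.** The Grade 1 deadline falls at week 4. A patient who resumed at Grade 2 in week 3 can be read as having ended his interruption in time. The text does not say whether the deadline still applies to him; that is a gap rather than a contradiction.
- **That 5.4.1 also conflicts.** It asks that toxicity "reverts to NCI CTCAE grade 1 or 2", but adds that the grade depends on the toxicity, which defers to the specific sections.
- **That power for the primary endpoint falls by a known amount.** That needs a removal rate, which the documents do not give. Under 7.6.3 only a patient with no assessment after starting treatment becomes a non-responder on that ground. PSA is scheduled on Day 1 of each cycle and at end of treatment, so most affected patients should have one, and a response documented before removal still counts.

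**Conclusion.** The conflict stands, limited to patients held 2 weeks or more for Grade 3 or worse anemia, neutropenia or thrombocytopenia (or with transfusion dependence) who are at Grade 2, without symptoms in the case of anemia, when the 4-week limit is reached. It is clearest for anemia.

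Its frequency cannot be estimated from the documents, and no effect on the primary response analysis is shown. The one quantified consequence, a change from 20% to 30% at 10 patients, would follow from any single reclassified patient. It shows that the stopping rule is sensitive to one patient and does not measure how often this conflict would move it. It rests on two assumptions: that 10.3.4 is applied to the observed proportion, and that the removal counts as one that followed dose modification. It should be fixed because it leaves a treatment-stopping rule undetermined for the toxicity the protocol expects most. Nothing here bears on which recovery grade is clinically appropriate.

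**What to change.** 1. Reconcile 5.4.4, 5.4.5 and 5.4.14 so that one recovery grade and one time limit apply to each cytopenia, or state explicitly which section governs once toxicity is prolonged. The clinical team chooses the grade. Check the result against the Day 1 criteria in 5.4.3.
2. Use the same 2-week trigger in all three sections.
3. State whether 5.4.14's deadline still applies to a patient who resumed at Grade 2 between weeks 2 and 4.
4. State in 10.3.4 whether a removal during a hold, with no prior dose reduction, counts toward the 25% rule.

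The cost is a protocol wording amendment and a notice to sites. Sample size, visits and data collection do not change. If patients have already been managed under these sections, their removals should be listed with the section applied, so that the 10.3.4 count can be restated on one definition.
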